Aims: To collect pilot data to establish the feasibility of a randomized controlled trial (RCT) of a manualized Compassion Meditation (CM) group treatment to restore functioning in older Veterans with psychological distress. Key questions include:

- (1) Will older Veterans with anxiety and/or depression enroll in and complete the proposed CM intervention?
- (2) What is the completion rate?
- (3) Do participants adhere to the treatment (complete practice at home)?
- (4) Are modifications required for the intervention to make it more acceptable and appropriate for older Veterans with emotional distress (e.g., length of session, pace of material, mechanism for supporting home

practice)?

(5) Does CM show promise for improving well-being, symptom severity, and/or positive psychological factors relevant to successful aging?

We also seek to optimize the assessment strategy for a future Merit Award application, including to explore feasibility of inflammatory biomarkers as a CM intervention outcome.

Section 7 - Background and Significance

7) Provide a succinct discussion of relevant background information to justify performing the proposed study.

Critical unmet need: Over the past decade, there has been unprecedented growth in the number of older Veterans who are at elevated risk for clinically significant emotional distress, but are less likely than younger Veterans to utilize specialty mental health VA clinics. These mental health concerns can result in considerable disability, medical comorbidity, higher health care utilization and costs, reduced physical and mental well-being, and higher mortality). The VA's Primary Care – Mental Health Integration (PCMHI) services are an important component in addressing such concerns, but older age remains associated with low mental health service utilization among psychologically distressed Veterans (Blais et al., 2015). If compassion-based interventions can be effectively tailored such that the benefits generalize to older

Veterans, then there is a unique opportunity for an evidence-based, novel treatment that not only reduces psychological distress, morbidity and mortality, but also promotes "healthy aging" and increases well-being (Jeste et al., 2015).

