9) Describe the research design and the procedures to be used to accomplish the specific aims of the project. Provide a precise description of the planned data collection (include what systems or databases will be used/accessed to gather data), analysis and interpretation. For chart review studies, include the timeframe of collection. Address sample size, inclusion of women and minorities. Define in clear terms exactly what will be done to the human subjects.

Participants: Participants will be up to 40 men and women Veterans in VASDHS ages 55 years or older who are self- and/or clinically identified through the Primary Care/PCMHI services with mild-to-moderate anxiety and/or depressive symptoms and meet the inclusion/exclusion criteria below.

Inclusion criteria: (1) VASDHS patient, (2) current age > 55 years, (3) current mild-to-moderate anxiety or depressive symptoms (as defined below), (4) stated intention to attend the 10 group sessions at the scheduled times at the VASDHS in addition to the baseline and follow-up study assessment visits, as well as to complete the outside homework assignments, and (5) provides written informed consent for participation.

Because this is a feasibility study and because all participants who enroll in the study will demonstrate capacity to consent to the research study, there will be no age limit.

Exclusion criteria: (1) No active suicidality/homicidality in the preceding six months, (2) untreated alcohol or substance use disorders (those co-enrolled in the VASDHS Alcohol and Drug Treatment Program will be eligible), (3) changes to psychiatric medications within six months of baseline evaluation (changes to medications during the course of the study will be permitted as determined appropriate by Veteran's treating clinicians, but changes will be recorded to further describe the sample), (4) medical and/or psychiatric instability interfering with current ability to engage in the group sessions and outside homework assignments.

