Descriptive statistics will be used to summarize the variables as well as to detect outliers and data entry errors. When applicable, normality of the distribution will be examined for outcome variables and residuals of regression model with a normal probability plot. The present project is intended as a feasibility study that will inform, support, and guide development of a subsequent larger-scale VA Merit Award project. Therefore, the primary analysis will be descriptive rather than hypothesis testing. Since the interventions are delivered by group (8-10 participants per group), it is possible that measured or unmeasured characteristics of the participants in a given group or their interactions may affect psychological response to the intervention, attendance, and study outcomes. The analysis plan described below is based on no cluster effect of class. But we will assess the impact of clustering effects by fitting a random effects model for each outcome, and, if necessary, a random class effect will be included in the model to account for the correlations between the individuals in the same class. The intraclass correlation coefficient (ICC) will also be estimated to understand the correlation within class and provide advice for sample size adjustment in future studies.

Will older Veterans with psychological distress [anxiety and/or depression] enroll in and complete the proposed CM intervention? What is the completion rate? Do participants adhere to the treatment (complete practice at home)? We will assess the following outcome measures for enrollment, completion, and adherence to treatment:

- 1) $\underline{\it Enrollment\ rate}$ defined as the proportion of consented subjects among all screened and eligible patients;
- 2) Initiation rate defined as the proportion of subjects who initiate the intervention among all consented subjects;
- 3) $\underline{Completion\ rate}$ defined as the proportion of subjects who complete 6 or more sessions (out of a total of 10 sessions) of intervention among those who start the intervention;
- 4) Practice time at home defined as average minutes that subjects practice at home each week. The mean (and SD) or percentage will be calculated and the 95% confidence intervals will be estimated for all outcomes.

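### The enrollment rate is taken over eligible patients, but eligibility already requires a stated commitment to the sessions and homework, and consent, so the rate is inflated or, read literally, fixed at 100%

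*Combined protocol and SAP*

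**What the plan says.** Section 6 (Specific Aims) opens its key questions with "Will older Veterans with anxiety and/or depression enroll in and complete the proposed CM intervention". The question is put for older Veterans with these symptoms, without restriction to those who promise attendance beforehand.

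The inclusion criteria in Section 9, repeated in Section 10, have five items. The first three describe the patient: VASDHS patient, age, and symptom range. The last two describe willingness. Item (4) is a "stated intention to attend the 10 group sessions at the scheduled times at the VASDHS", together with the assessment visits, "as well as to complete the outside homework assignments". Item (5) is that the Veteran "provides written informed consent for participation".

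The Analytic plan in Section 9 defines the enrollment rate as "defined as the proportion of consented subjects among all screened and eligible patients". The completion rate is "the proportion of subjects who complete 6 or more sessions" out of 10, "of intervention among those who start the intervention". Adherence is "average minutes that subjects practice at home each week". The Sample size assessment names the enrollment and completion rates as the primary outcomes and cites earlier rates between 0.57 and 0.82.

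**The concern.** An enrollment rate is meant to show how many of the people who could join do join. Here the willingness to join is part of the test for entering the denominator. A Veteran who has the right age and symptoms, meets no exclusion, and says that ten weeks or the homework is too much fails criterion (4). By the stated definition that person is ineligible and is not counted as someone who declined. No other part of the document counts these Veterans, records their reasons, or sets up a second denominator.

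The later RCT will be planned from this rate. If it is overstated, the number of Veterans who must be screened to fill a class is understated. The planned analysis of which patient characteristics go with enrollment also loses these refusers. So does the question in Section 6 of whether session length, pace or home-practice support should be changed, because the satisfaction measures and post-intervention interviews reach participants only.

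**Working it through.** The plan gives no figure for the share of Veterans who fail criterion (4), so there is no stated value to reproduce. The only related figure is the planning range of 0.57 to 0.82 in the Sample size assessment, and the text does not say how the denominators behind it were formed.

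**Step 1: the literal reading.** Eligible means meeting (1) to (5) with no exclusion. Criterion (5) is consent, so everyone in the denominator has consented. Section 10 expects no screen failures among those who consent, so the numerator is the same set of people. The rate is 1 whatever happens in recruitment.

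**Step 2: criterion (5) set aside, criterion (4) kept.** Let N be the screened Veterans who meet (1) to (3) and no exclusion, c the share of N who will not state the commitment, and E the number who consent, all of whom stated it.

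- Rate with refusers kept in the denominator: E/N
- Rate as defined: E/[N(1-c)]
- Ratio of the second to the first: 1/(1-c)

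The values of c below are assumptions. The last two columns multiply the ends of the planning range by (1-c), to show what a reported rate of that size would mean once refusers are restored.

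| c | Inflation 1/(1-c) | Reported 0.82 becomes | Reported 0.57 becomes |
|---|---|---|---|
| 10% | 1.11 | 0.738 | 0.513 |
| 20% | 1.25 | 0.656 | 0.456 |
| 30% | 1.43 | 0.574 | 0.399 |
| 40% | 1.67 | 0.492 | 0.342 |

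At c = 30%, 0.82 x 0.70 = 0.574, which is the whole distance from the top to about the bottom of the planning range.

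In counts, suppose 60 otherwise eligible Veterans and 30 consents (both numbers assumed), a rate of 30/60 = 0.50. With c = 10%, 6 are removed and the reported rate is 30/54 = 0.56. With c = 40%, 24 are removed and it is 30/36 = 0.83.

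**Step 3: completion and practice time.** Criterion (4) selects on what a Veteran says before starting. Completion is observed attendance at 6 or more of 10 sessions among starters, and adherence is observed minutes. Both can still turn out low in people who stated the intention. No inflation factor follows from the definitions alone. An upward shift relative to all older Veterans with these symptoms would need the further assumption that those who decline the commitment would attend and practise less.

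**The case against.** The strongest reply is that nobody would read eligible so literally. Since criterion (5) would make the rate meaningless, the authors must mean eligible apart from willingness, and criterion (4) is as much a matter of willingness as (5). That may well be the intention, but the document does not say so. The argument shows that the denominator fails as written; it does not supply the one to use.

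It is also fair that the documents do not say when criterion (4) is asked. Section 11 describes chart review, a telephone screen for immediate exclusions, and then a Baseline Visit for consent and eligibility. Staff might log a Veteran who will not commit as a decliner. A reader might therefore infer too much by saying that refusers will certainly be dropped in practice. What the text supports is that the definition classes them as ineligible and that nothing provides otherwise. The factor 1/(1-c) applies to the extent that they are classed that way.

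A reader might also infer that completion and adherence are measured in Veterans pre-selected on those very outcomes. The documents do not support this: selection is on stated intention, and completion among starters is an openly stated definition. If the later RCT keeps criterion (4), completion among committed Veterans is the rate that it needs.

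Nor do the documents support the reading that the rule hides the main barrier the study was set up to find. The barrier they stress is perceived stigma, not session burden.

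Two practical objections stand. Criterion (4) also covers availability at fixed times, so failing it mixes diary conflicts with refusal of the intervention. And the first cohort was already in its sessions when the COVID-19 updates were written, so a new screening field cannot reach it.

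**Conclusion.** The concern holds for the enrollment rate. Its denominator includes two willingness items, which makes the rate 100% on the literal reading and inflated by 1/(1-c) if only criterion (5) is ignored. The direction is certain whenever c is above zero and those who will not commit are classed as ineligible. The size is not known: the factor of 1.11 to 1.67 rests on an assumed c of 10% to 40%, and the counts of 60 and 30 are illustrative. The concern does not extend to a claim of bias in completion or practice time. For those it is enough to name the group to which they apply.

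**What to change.** Keep criterion (4) as a condition for joining a class, and change the definition of the rate in the Analytic plan:

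- Define the enrollment denominator as all screened Veterans who meet criteria (1) to (3) and no exclusion. Count those who fail only (4) or (5) as eligible non-enrollers.
- Tabulate the reasons for non-enrollment, separating a scheduling conflict from refusal of the session burden or the homework burden.
- Also report the rate among Veterans who stated the commitment, since a later RCT with the same criterion will need it.
- Apply this prospectively to the remaining cohorts. For the first cohort, use existing screening records where they allow it, and say where they do not.
- State that completion and practice time describe Veterans who said in advance that they intended to attend and do the homework.

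The cost is a rewording of one definition, one extra field on the screening log, and an enrollment rate that will look less favourable. The conditions for joining a class stay the same.

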As part of their clinical connection to PCMHI all participants will have completed the PHQ-9, which includes a question about thoughts of death during the past 2 weeks, but we will also directly ask potential participants if they have had suicidal ideation, or thoughts of harming others, with a plan or intention within the past year. If enrolled, participants also sign a HIPAA permitting us to examine CPRS records. The CPRS has mandatory annual suicide risk screening, flags for patients deemed high risk suicide, and mandatory Suicide Behavior Reports suicidal behavior not previously documented in the CPRS, as well as disruptive behavior flags and reports.

Suicidality/homicidality in the preceding six months: As part of their clinical connection to PCMHI all participants will have completed the PHQ-9, which includes a question about thoughts of death during the past 2 weeks, but we will also directly ask potential participants if they have had suicidal ideation, or thoughts of harming others, with a plan or intention within the past year. If enrolled, participants also sign a HIPAA permitting us to examine CPRS records. The CPRS has mandatory annual suicide risk screening, flags for patients deemed high risk suicide, and mandatory Suicide Behavior Reports suicidal behavior not previously documented in the CPRS, as well as disruptive behavior flags and reports.

Cognitive impairment and decisional capacity: Capacity to consent to research is an important issue in ensuring that voluntary consent is authentic and valid. This is an issue [name] has studied extensively (e.g. see MCIDs: PMC5279898, PMC6085078, and PMC3382031). Given the minimal risk nature of this study, we will not explicitly assess cognitive or decisional capacity. However, [name] will train the staff obtaining informed consent in procedures (such as pausing after describing the study purpose and asking the potential participant to explain the purpose of the study in their own words – see [name] et al. "effective use of consent forms and interactive questions in the consent process" PMID: 18512654). Staff will be trained to be alert to participants who do not appear to understand the overall purpose of the study and the nature of the compassion meditation or psychoeducational groups, that this is a research project, or that participation is completely voluntary. Participants, who do not appear able to understand these basics, even after re-explanations, will not be enrolled.

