Potential participants will be recruited through the VASDHS PCMHI program. The investigators will inform the clinical providers of the PCMHI clinics about the study and will provide VASDHS IRB-approved Provider Referral Information sheets, which will assist referring providers in identifying and referring potential participants to the study. Referring PCMHI clinicians who are meeting individually with potential Veteran participants may indicate Veteran interest in participation through a VA-encrypted email or a separate (or addendum to clinical visit) CPRS note using the text template below:

CPRS note: "Veteran is willing to be contacted by phone regarding CBCT study (PI [name]) by the PI or study staff." Provider will add [name] to CPRS note to alert us to its presence.

In addition, PCMHI providers will be given our IRB-approved participant brochure summarizing the project that can be given to appropriate patients to call our study staff for further information about the study.

Screening:

We request a partial HIPAA waiver to conduct pre-screening CPRS chart review for all interested participants to ensure there are no immediate exclusion criteria noted prior to initiating contact with interested participants via phone (see Protocol Section 12).

Individuals who agree to be contacted by phone by the PI or study staff, as well as those who call our study phone number, will be asked to provide verbal consent to participate in a brief telephone screen (see attached Oral Consent/Phone Screen form). If no immediate exclusions are identified via the telephone screen, participants will be scheduled to come in for an in-person study visit (i.e., "Baseline Visit"), to review and discuss the information in the IRB-approved informed consent and HIPAA documents, and to be screened to determine eligibility to participate in the Compassion Meditation sessions

During the Baseline Visit, [name], [name], or [name], or an appropriately trained RA under our supervision will meet with the participant to review and discuss the information in the IRB-approved informed consent and HIPAA documents. Participants will be provided with an opportunity to read the consent document and/or to have it read to them. After thorough discussion, including answering any questions from the potential participant, willing participants will be asked to sign the informed consent and HIPAA documents to indicate their consent to participate.

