Equity will be fostered by adherence to the inclusion/exclusion criteria listed above as the basis for enrollment. As part of the informed consent process, potential participants will be informed that participation is entirely voluntary so as to minimize any potential feelings of coercion or undue influence.

Section 11.1 Recruitment Materials

11.1) Identify all recruitment materials (flyers, advertisements, letters, etc.) that will be used; include the web address for any web-based advertisements. The text of all communications with prospective participants must be reviewed and approved by the IRB before it can be used. You will be reminded to attach copies of recruitment materials to the initial submission packet.

Note: Posting of flyers with pull tabs is not permitted within VASDHS (including the VMRF building).

The recruitment materials will include a VASDHS IRB-approved Provider Referral Information sheet, which will be given to PCMHI referring providers only, as well as an IRB-approved participant brochure that may be given to potential Veterans participants. Any additional recruitment materials will be submitted as protocol amendments for IRB review and approval; no recruitment materials will be used unless and until approved by the VASDHS IRB.

Section 12 - Informed Consent

12)	Indicate	whether	or not	each ca	tegory (of consent	is in	volved	in thi	s study:

12a) Will the study team obtain information or biospecimens for the purpose of screening, recruiting, or determining the eligibility of prospective subjects without (or prior to) obtaining informed consent of the prospective subject or the prospective subject's LAR?

⊙ Yes ○ No

Check one or both of the below boxes if they apply to this study:

Overall, risks of harm from this protocol itself appear unlikely and/or are unlikely to result in enduring harm or disability.

Section 15 - Risk Management

15) Describe the procedures for protecting against or minimizing any potential risks/discomforts, and the adequacy of resources for conducting the study and resources participants may need as a consequence of the research. When applicable, include detail of the following safety measures:

(a) The type of safety information to be collected, including AEs;
(b)

Frequency of safety data collection; (c) Frequency or periodicity of review of cumulative safety data;

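### Exclusion criterion (1) is inverted as written in Sections 9 and 10: it lists the absence of suicidality/homicidality as the reason to exclude

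*Combined protocol and SAP*

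**What the plan says.** The protocol gives its eligibility criteria twice, in Section 9 (Design and Methods) and in Section 10 (Human Subjects). The first exclusion item is the same in both: "Exclusion criteria: (1) No active suicidality/homicidality in the preceding six months". The remaining items of the Section 9 list, repeated in Section 10, are:

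- "2) untreated alcohol or substance use disorders"
- "3) changes to psychiatric medications within six months of baseline evaluation"
- "4) medical and/or psychiatric instability interfering with current ability to engage in the group sessions"

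Section 9 then has an explanatory paragraph on the first criterion. It begins "Suicidality/homicidality in the preceding six months: As part of their clinical connection to PCMHI" and lists what staff will draw on: the PHQ-9, a direct question to the potential participant, and risk flags and reports in the VA record system.

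Section 11 (Recruitment) says how the criteria are used. On selection it states: "Equity will be fostered by adherence to the inclusion/exclusion criteria listed above as the basis for enrollment". Before any telephone contact, charts are reviewed "to ensure there are no immediate exclusion criteria noted prior to initiating contact with interested participants via phone". A telephone screen and an eligibility check at the baseline visit follow.

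**The concern.** An exclusion list states what keeps a person out. An item in that list that begins with a negation keeps out people who lack the condition. Applied exactly as printed, item (1) would turn away Veterans with no recent suicidality or homicidality and would raise no bar to those with it.

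This is a safety criterion, and it is the only listed criterion that names suicidality or homicidality. Item (4) might catch some of the same people, but only where instability interferes with taking part in sessions and homework. The list is what staff, monitors and auditors check enrollment against. As it stands, conduct that follows the evident intent departs from the printed rule. The study is also meant to prepare a larger randomized trial, so its eligibility text may be carried forward.

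**Working it through.** No arithmetic applies. The check sets the relevant texts side by side.

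1. **Item (1), Section 9.** It stands under the exclusion heading and opens with a negation. Literal effect: absence of the condition excludes.
2. **Item (1), Section 10.** The wording and heading are identical, so the literal effect is the same. Because the same intact sentence appears in two separate sections, an error in reading the PDF is unlikely. Neither place is an amendment log or marked as redacted.
3. **Items (2), (3) and (4), both lists.** Each names something whose presence excludes: an untreated disorder, a recent medication change, an interfering instability. None is negated. Item (1) is the only one that runs the other way.
4. **Explanatory paragraph, Section 9.** Its heading names the same condition and the same six-month period as item (1), without the negation. The sources it lists all look for presence of the condition. It therefore points in the opposite direction to the literal text of item (1).
5. **Does the explanatory paragraph correct the list?** Not expressly. It describes what is asked and which records exist, but it does not say which answer leads to exclusion. That decision is stated only in the two lists.
6. **Does any other text correct it?** None was found. Section 11 refers back to the listed criteria and does not restate them.
7. **Are the lists operative?** Yes. Section 11 makes them the basis for enrollment and describes three steps at which exclusions or eligibility are checked: chart pre-screen, telephone screen and baseline visit.

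Item (1) as printed thus contradicts both the form of its own list and the heading of the paragraph written to explain it.

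**The case against.** The best reply is that this is a slip that the document itself resolves. The Section 9 paragraph drops the negation and describes looking for presence. The literal rule would admit only Veterans with active suicidality or homicidality, which cannot be squared with a study that Section 9 calls minimal risk and that enrolls people with mild-to-moderate symptoms. No sensible reader would apply it. The telephone-screen form is not among the documents, so nothing shows that the error reached a working screening tool.

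Most of this stands. The intent is readable, and the documents do not show that any form repeats the error. What does not follow is that the text may be left alone: a safety criterion should state its rule correctly, and a reader should not have to infer it from a nearby heading.

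A reader might also infer a second contradiction, because the direct question in Section 9 asks "if they have had suicidal ideation, or thoughts of harming others, with a plan or intention within the past year" while the criterion covers six months. The documents do not support that. A one-year question takes in the whole six-month window, so nobody inside the window is missed because of the look-back. A screening question may be broader than the criterion it serves. How an answer maps to a decision may be set out in the telephone-screen form, which is not available here.

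**Conclusion.** The point holds: exclusion criterion (1) is inverted as written in Sections 9 and 10. Confidence is high on the wording, which can be checked directly. It rests on two premises: that an exclusion list names what bars entry, as items (2) to (4) do, and that the Section 9 heading shows the intended direction.

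The practical effect is expected to be small, since staff who read the whole list or the explanatory paragraph are unlikely to be misled. A reader might infer that the wrong Veterans would be enrolled or that the enrollment rate would be distorted. The documents do not support either inference: nothing in them shows staff screening from the literal text, and they give no figure from which to estimate a number affected. No sample size, margin of error, power figure or analysis depends on this wording. It merits correction because it is an operative safety rule, not because it changes a result.

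**What to change.** Reconcile item (1) in the Section 9 and Section 10 exclusion lists with items (2) to (4) and with the heading of the explanatory paragraph in Section 9, so that it names the presence of the condition. Check that the telephone-screen form reads the same way. How the condition is defined, and over what period, remains for the investigators to decide.

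The cost is a one-word correction in two places and one check of an existing form. Sample size, data collection and analysis are unaffected.
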